13.1.3. Hexsel Cellulite Severity Scale

The Hexsel Cellulite Severity Scale (referred to as the Hexsel CSS) is a photonumeric scale that looks at 5 key morphologic features of cellulite: (A) number of evident depressions, (B) depth of depressions, (C) morphological appearance of skin surface alterations, (D) laxity, flaccidity or sagging of skin, and (E) current classification scale based on medical literature including Nürnberger and Müller.(12,13) Each of these features is evaluated on a 4-level scale from a low of 0 to a high of 3 as described in [Table 7 \(Appendix D and Appendix E\)](#). The total score is the summation of all 5 features.

The Investigator or qualified designee will independently use the Hexsel CSS to assess the severity of EFP in each of the 4 treatment areas at the Screening visit and each of the two assigned treatment areas on Day 1. All cellulite assessments should be made while the subject is in the standing position with relaxed gluteus muscles. However, when evaluating the subject for Category E (classification scale by Nürnberger and Müller) (13) if the subject has no evident depressions, the subject should be asked to contract her gluteus muscles or the pinch test should be applied (by pinching the skin between the thumb and index finger) so the Investigator or qualified designee can differentiate between scores/grades of zero (0) or I.

Table 7: Hexsel Cellulite Severity Scale

A	Number of evident depressions	0=none/no depressions 1=a small amount: 1-4 depressions are visible 2=a moderate amount: 5-9 depressions are visible 3=a large amount: 10 or more depressions are visible
B	Depth of depressions	0=no depressions 1=superficial depressions 2=medium depth depressions 3=deep depressions
C	Morphological appearance of skin surface alterations	0=no raised areas 1='orange peel' appearance 2='cottage cheese' appearance 3='mattress' appearance
D	Grade of laxity, flaccidity, or sagging skin	0=absence of laxity, flaccidity, or sagging skin 1=slight draped appearance 2=moderate draped appearance 3=severe draped appearance
E	Classification scale by Nürnberger and Müller ^a	0 = zero grade = Grade or Stage 0 = There is no alteration of the skin surface. 1 = first grade = Grade or Stage I = The skin of the affected area is smooth while the subject is standing or lying, but the alterations to the skin surface can be seen by pinching the skin or with muscle contraction. 2= second grade = Grade or Stage II = The orange skin or mattress appearance is evident when standing, without the use of any manipulation (skin pinching or muscle contraction). 3= third grade = Grade or Stage III = The alterations described in Grade or Stage II, are present together with raised areas and nodules.

Source: Hexsel DM, Dal'Forno T, Hexsel CL. A validated photonumeric cellulite severity scale. *J Eur Acad Dermatol Venereol.* 2009;23(5):523-8.

^a Subjects should be evaluated in the standing position with relaxed gluteus muscles. However, if the subject has no evident depressions, they should be asked to contract their gluteus muscles or the pinch test should be applied (by pinching the skin between the thumb and index finger) in order to differentiate between grade/stage of zero (0) or I.

14. ASSESSMENT OF SAFETY

14.1. Definitions

14.1.1. Adverse Events

An adverse event (AE) is any unfavorable or unintended change in body structure (signs), body function (symptoms), laboratory result (eg, chemistry, ECG, X-ray, etc.), or worsening of a pre-existing condition associated temporally with the use of the study medication whether or not considered related to the study medication. Adverse events will be captured once a subject has signed the informed consent. AEs include:

- Changes in the general condition of the subject
- Subjective symptoms offered by or elicited from the subject
- Objective signs observed by the Investigator or other study personnel
- All concurrent diseases that occur after the start of the study, including any change in severity or frequency of pre-existing disease
- All clinically relevant laboratory abnormalities or physical findings that occur during the study

A treatment-emergent AE (TEAE) is any condition that was not present prior to treatment with study medication but appeared following treatment, was present at treatment initiation but worsened during treatment, or was present at treatment initiation but resolved and then reappeared while the individual was on treatment (regardless of the intensity of the AE when the treatment was initiated).

All AEs, including both observed or volunteered problems, complaints, signs or symptoms must be recorded on the AE page of the eCRF, regardless of whether associated with the use of study medication. This would include AEs resulting from concurrent illness, reactions to concurrent medication use, or progression of disease states (excluding the disease under study). A condition present at baseline that worsens after initiation of study treatment will be captured as an AE; the onset date will be the date the event worsened. The AE should be recorded in standard medical terminology when possible.

14.1.2. Serious Adverse Events

A serious adverse event (SAE) is defined as an AE that:

- Results in death
- Is immediately life-threatening (there is an immediate risk of death from the AE as it occurred; this does not include an AE that had it occurred in a more serious form may have caused death)
- Results in or prolongs an inpatient hospitalization (Note: a hospitalization for elective or pre-planned surgery, procedure, or drug therapy does not constitute an SAE)

- Results in permanent or substantial disability (permanent or substantial disruption of one's ability to conduct normal life functions)
- Is a congenital anomaly/birth defect (in offspring of a subject using the study medication regardless of time to diagnosis)
- Is considered an important medical event

Important medical events are defined as events that, based upon appropriate medical judgment, may jeopardize the subject and may require medical or surgical intervention to prevent one of the other serious outcomes. Examples of important medical events include malignancy, allergic bronchospasm requiring intensive treatment in an emergency room or at home, blood dyscrasias or convulsions that do not result in inpatient hospitalization, or the development of drug dependency or drug abuse.

14.2. Monitoring Adverse Events

At each visit, subjects will be queried regarding any AEs that have occurred since the last visit. Subjects will be asked to volunteer information concerning AEs with a non-leading question such as, "How do you feel?" Study site personnel will then record all pertinent information in the source documents and the eCRF. The study drug compliance record should also be reviewed to detect potential overdoses (intentional/unintentional).

14.3. Relationship to Study Drug

The degree of "relatedness" of the AE to the study medication must be described using the following scale:

- **Not related** indicates that the AE is definitely not related to the study medication.
- **Unlikely related** indicates that there are other, more likely causes and study medication is not suspected as a cause.
- **Possibly related** indicates that a direct cause and effect relationship between study medication and the AE has not been demonstrated, but there is evidence to suggest there is a reasonable possibility that the event was caused by the study medication.
- **Probably related** indicates that there is evidence suggesting a direct cause and effect relationship between the AE and the study medication.

It is the Sponsor's policy to consider "Probably related" and "Possibly related" causality assessments as positive causality. "Not related" and "Unlikely related" causality assessments are considered as negative causality.

Assessments will be recorded on the eCRF and must indicate clearly the relationship being assessed. For example, an AE that appears during a placebo run-in phase would be assessed with respect to the placebo treatment received and/or study procedures conducted during this phase. If the AE continued into an active treatment phase, the relationship would be assessed for the active treatment phase only if the AE worsened.

14.4. Intensity Assessment

The intensity (or severity) of AEs is characterized as mild, moderate, or severe:

- **Mild** AEs are usually transient, requiring no special treatment, and do not interfere with the subject's daily activities.
- **Moderate** AEs introduce a low level of inconvenience or concern to the subject and may interfere with daily activities, but are usually ameliorated by simple therapeutic measures.
- **Severe** AEs interrupt a subject's usual daily activity and typically require systemic drug therapy or other treatment.

When the intensity category of an AE changes, the greatest intensity during that continuous episode should be recorded.

14.5. Reporting Adverse Events and Serious Adverse Events

14.5.1. Reporting Adverse Events

Throughout the study, AEs will be documented on the source document and on the appropriate page of the eCRF whether or not considered treatment-related. This includes any new signs, symptoms, injury or illness, including increased severity of previously existing signs, symptoms, injury, or illness. Conditions existing prior to screening will be recorded as part of the subject's medical history. The Investigator is responsible for assessing the relationship of AEs to the study medication; relationship will be classified as not related, unlikely related, possibly related, or probably related.

All AEs will be collected by the Investigator from the time of signing the informed consent through 28 days after the last dose of study medication; this includes any AEs that are ongoing at the time of completion/termination of the study. All ongoing AEs must be followed until resolution or for 30 days after the subject's last study visit, whichever comes first.

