5. SCHEDULE OF EVENTS

Procedures	Day -14 to -1 Screening	Day 1 (Baseline)	Post-Injection Day				Day 22 (±3 d)	Post-Injection Day				Day 43 (± 3 d)	Post-Injection Day				Day 90 (± 7d)	Day 180 (+ 7 d) EOS/ ET	Unsched. Visit
			1	3	6	13		1	3	6	13		1	3	6	13			
Informed Consent	X																		
Inclusion/Exclusion	X																		
Medical history/EFP history including previous treatments	X																		
Prior/concomitant medications/procedures	X	X	X	X	X	X	X	X	X	X	X	X	X	X	X	X	X	X	
Physical examination:	X																		
• Body weight	X						X ^a					X ^a				X	X	X	
• Height	X																		
• Fitzpatrick skin type	X																		
Vital signs	X	X ^b					X ^b					X ^b				X	X	X	
12-lead ECG	X																		
Digital Photography ^c		X	X	X	X	X	X	X	X	X	X	X	X	X	X				
Medical status follow-up			X	X	X	X		X	X	X	X		X	X	X	X			
Laboratory Assessments																			
• Clinical laboratory	X																X	X	
• Anti-AUX-I/anti-AUX-II antibody level		X ^a					X ^a					X ^a				X	X		
• Pregnancy testing	X ^f	X ^{a,f}					X ^{a,f}					X ^{a,f}				X ^f	X ^f	X	
Subject Cellulite Assessments																			
• Subject Satisfaction With Cellulite Treatment Assessment																	X ^g		
Investigator Cellulite Assessments																			
• Selection and marking of dimples to be treated within both assigned treatment areas		X ^a					X ^a					X ^a							
• Clinician Reported Photonumeric Cellulite Severity Scale (CR-PCSS)	X						X ^{a,e}					X ^{a,e}				X ^e	X ^e		
• Hexsel Cellulite Severity Scale (CSS)	X ^d																		
• Confirm Eligibility																			
• Assign Region	X																		
• Study drug administration		X					X					X							

Procedures	Day -14 to -1 Screening	Day 1 (Baseline)	Post-Injection Day				Day 22 (±3 d)	Post-Injection Day				Day 43 (± 3 d)	Post-Injection Day				Day 90 (± 7d)	Day 180 (+ 7 d) EOS/ET	Unsched. Visit
			1	3	6	13		1	3	6	13		1	3	6	13			
• Injection site reactions/local tolerability in assigned treatment areas		X	X	X	X	X	X	X	X	X	X	X	X	X	X	X	X		
• Adverse events	Monitored Throughout Study																		

- ^a Before injection.
 - ^b Up to 4 hours before injection; approximately 15 and 30 minutes after injection. Pulse and BP to be taken after subject has been sitting for 5 minutes. Vital signs must be stable before the subject is discharged.
 - ^c Applies only to sites participating in the photography sub-study. Photos are to be obtained before and after dimple marking on treatment visits.

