12.6. Day 90 (± 3 days)

The following procedures will be performed on Day 90:

1. Record concomitant medications/procedures (section 12.9)
2. Measurement of body weight
3. Vital sign measurements (section 14.9)
4. Collection of samples for:
 - a. Anti-AUX-I and anti-AUX-II antibody testing (section 14.8)
 - b. Urine pregnancy testing (section 14.7)
5. Investigator Cellulite Assessments of each of the assigned treatment areas using:
 - a. Clinician Reported Photonumeric Cellulite Severity Scale (CR-PCSS) live assessment of subject (section 13.1.1)

6. Injection site reactions and local tolerability
7. Adverse events (section 14)

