14.5.2. Reporting Serious Adverse Events

Any SAE, including death resulting from any cause, which occurs to any subject participating in this study must be reported via email or fax by the Investigator using the Endo Clinical Trial Report Form for SAEs within 24 hours of first becoming aware of the SAE. SAEs will be collected by the Investigator from the time of signing the informed consent through 28 days after the last dose of study medication. SAEs that occur within 28 days, following cessation of the study treatment, or within 30 days, following premature discontinuation from the study for any reason, must also be reported within the same timeframe. Any SAE that is felt by the Investigator to be related to the study medication must be reported regardless of the amount of time since the last dose received. Follow-up information collected for any initial report of an SAE must also be reported to the Sponsor within 24 hours of receipt by the Investigator.

All SAEs will be followed until resolution, stabilization of condition, or until follow-up is no longer possible.

In the event discussion is necessary regarding treatment of a subject, call the Medical Monitor (see contact information in section 3).

All SAEs should be sent via the email address, or faxed to the fax number, provided in section 3.

The Sponsor will determine whether the SAE must be reported within 7 or 15 days to regulatory authorities in compliance with local and regional law. If so, the Sponsor (or the Sponsor's representative) will report the event to the appropriate regulatory authorities. The Investigator will report SAEs to the Institutional Review Board (IRB) per their IRB policy.

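### Protocol 14.5.1 and 14.5.2 end AE and SAE collection 28 days after the last dose, while the same sections and the rest of the plan carry it to Day 180

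*Protocol*

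**What the plan says.** Two sentences set a 28-day limit. Protocol 14.5.1: "All AEs will be collected by the Investigator from the time of signing the informed consent through 28 days after the last dose". Protocol 14.5.2: "SAEs will be collected by the Investigator from the time of signing the informed consent through 28 days", again counted from the last dose.

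Other sentences in the same two sections go further:

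- 14.5.1 opens with "Throughout the study, AEs will be documented on the source document and on the appropriate page of the eCRF". Its 28-day sentence goes on to include AEs still ongoing when the study is completed, which for a completer is Day 180.
- 14.5.2 opens with "Any SAE, including death resulting from any cause, which occurs to any subject participating in this study must be reported". It also covers SAEs "within 30 days, following premature discontinuation from the study for any reason, must also be reported within the same timeframe", and it makes SAEs judged related reportable however long after dosing they occur.

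Elsewhere the plan collects AEs to the end of the study:

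- The adverse-event row of the Schedule of Events (Protocol section 5, repeated in SAP Table 1) reads "Monitored Throughout Study".
- Protocol 14.2: "At each visit, subjects will be queried regarding any AEs that have occurred since the last visit".
- The Day 90 and Day 180 procedure lists (12.6 and 12.7) each contain an item beginning "Adverse events (section 14".
- Protocol 17.1 and SAP 3.7 base the sample size of up to 150 on six months of monitoring.
- SAP 3.2.6.1.1 assigns to Treatment Session 3 every AE starting from the Day 43 visit to the Day 180 visit. SAP 3.2.6.1 defines a treatment-emergent AE (TEAE) by its start date alone, with no end date.

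**The concern.** The two readings give different data sets, and no text ranks them. The Schedule does not settle it: the Day 90 and Day 180 lists refer the site to section 14, which contains the 28-day limit.

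Safety is the primary objective (Protocol 9.1), and the main output is the proportion of subjects with each event. If sites read 14.5 differently, the TEAE tables would combine subjects observed for new AEs to about Day 71 with subjects observed to Day 180, all in one safety-population denominator. The data would not distinguish a subject with no late event from one whose late event was not recorded. The study has a single arm and about 10 sites, so no control group would expose the shortfall. Events not recorded at the time are hard to recover later.

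One other instruction also conflicts with the limit. Protocol 14.7 requires laboratory abnormalities that meet the potentially-clinically-important criteria to be recorded as AEs or SAEs. The only scheduled clinical laboratory draw after dosing is at Day 180 or early termination (Schedule of Events; SAP 3.1.15). For a completer, an abnormality first found at that draw lies outside the 28-day window.

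**Working it through.** The plan states no figure for the length of AE collection, so the check is day arithmetic.

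**Inputs**

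- Dosing on Days 1, 22 and 43, with ±3 days on the second and third (Protocol 12.5).
- Collection limit: last dose + 28 days (14.5.1, 14.5.2).
- End of follow-up: Day 180, with +7 days allowed (section 5; 12.7).
- Day 90 visit: ±7 days in the Schedule of Events, ±3 days in 12.6.
- Last post-injection contact: 13 days after dosing in section 5 and 12.4, but 14 days in 12.13.

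Timeline check: 14 days of screening + 180 = 194 days, the stated study duration.

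**Formulas**

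Window end = last-dose day + 28. Uncovered days = 180 − window end. Share = uncovered days / 180.

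| Last dose | Window end | Uncovered to Day 180 | Share |
|---|---|---|---|
| Day 43 | 43 + 28 = 71 | 180 − 71 = 109 | 60.6% |
| Day 40 (−3) | 68 | 112 | 62.2% |
| Day 46 (+3) | 74 | 106 | 58.9% |
| Day 22 | 50 | 130 | 72.2% |
| Day 1 | 29 | 151 | 83.9% |

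If the final visit falls on Day 187, the Day 43 case leaves 187 − 71 = 116 days. Across the dosing window the range is 187 − 74 = 113 to 187 − 68 = 119 days.

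The Day 22 and Day 1 rows apply to a subject who stays in follow-up without further injections. Protocol 12.2 allows this when both areas are rated 0.

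**Which AE queries fall outside the window (last dose on Day 43)**

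- With the last contact on Day 43 + 13 = 56, the Day 90 query covers Days 57–90, which is 34 days. Days 72–90, which is 19 days, lie outside the window. With the 14-day contact of 12.13 (Day 57), it is 19 of 33 days.
- The Day 180 query covers Days 91–180, which is 90 days, all outside.
- Total: 19 + 90 = 109, matching the table.

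**Whether the Day 90 visit can fall inside the window**

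The latest window end is Day 74. The earliest Day 90 visit is Day 83 (±7) or Day 87 (±3), so the gap is 83 − 74 = 9 days or 87 − 74 = 13 days. Both post-treatment follow-up visits therefore always lie outside the 28-day window.

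**The case against.** The strongest reply is that 28 days is a minimum tail, meant mainly for subjects who leave early. The opening of 14.5.1 and the clause on AEs ongoing at completion can be read that way. The text does not say so, however: a period running from consent through a fixed number of days after dosing reads as a closed window. The clause on ongoing AEs adds to the inconsistency, because completion is at Day 180.

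A second reply is that most of the protocol points to Day 180, so sites will keep collecting. Safety is to be assessed throughout, 14.1.1 requires all AEs to be recorded, and injection-site reactions have their own prompt at Day 90 and Day 180. The protocol also reports that most earlier AEs were local and resolved before the next treatment. This stands as a limit on the likely harm. The exposure is mainly late AEs that are not injection-site reactions, and the day counts are a worst case.

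The SAE part is weaker than the AE part, and that also stands. The opening duty in 14.5.2 is unrestricted, the post-treatment provisions are worded as additional, and related SAEs have no time limit. Only SAEs judged unrelated are arguably affected.

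The rows for a last dose on Day 1 or Day 22 are edge cases. An end date in the SAP's TEAE definition is helpful but not essential once collection itself is bounded.

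**Conclusion.** The contradiction is real and should be fixed. It lies within 14.5.1 and 14.5.2 and between those sections and the rest of the protocol and SAP.

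For a subject dosed on schedule, the 28-day sentences leave 109 of 180 days (61%) uncovered. The figure is 106 to 112 days over the dosing window, and up to 119 days if the final visit is on Day 187. These figures assume a site applies only the 28-day sentences. They measure calendar time, and the documents give no basis for converting them into missed events. The conclusion is firm for non-serious AEs and qualified for SAEs, where only those judged unrelated are in doubt. The design plainly intends follow-up to Day 180; the defect is in the wording of the collection rule.

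**What to change.** Give 14.5.1 and 14.5.2 one data-collection window: all AEs and SAEs from informed consent through the Day 180/end-of-study/early-termination visit, or 28 days after the last dose if that is later. Keep the 14.5.2 provisions for related SAEs at any time and for SAEs within 30 days of premature discontinuation. This agrees with Protocol sections 5, 12.6, 12.7, 14.2 and 17.1 and with SAP 3.2.6.1.1. Optionally, state the same end point in the TEAE definition in SAP 3.2.6.1.

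The cost is a protocol amendment, with IRB approval and a signed investigator page before use (Protocol 21.1), and some additional eCRF entries for late AEs. No new visits or procedures are needed, since the Day 90 and Day 180 visits and their AE queries already exist. The change is best made before subjects pass about Day 71.

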14.5.2. Reporting Serious Adverse Events

Any SAE, including death resulting from any cause, which occurs to any subject participating in this study must be reported via email or fax by the Investigator using the Endo Clinical Trial Report Form for SAEs within 24 hours of first becoming aware of the SAE. SAEs will be collected by the Investigator from the time of signing the informed consent through 28 days after the last dose of study medication. SAEs that occur within 28 days, following cessation of the study treatment, or within 30 days, following premature discontinuation from the study for any reason, must also be reported within the same timeframe. Any SAE that is felt by the Investigator to be related to the study medication must be reported regardless of the amount of time since the last dose received. Follow-up information collected for any initial report of an SAE must also be reported to the Sponsor within 24 hours of receipt by the Investigator.

All SAEs will be followed until resolution, stabilization of condition, or until follow-up is no longer possible.

In the event discussion is necessary regarding treatment of a subject, call the Medical Monitor (see contact information in section 3).

All SAEs should be sent via the email address, or faxed to the fax number, provided in section 3.

The Sponsor will determine whether the SAE must be reported within 7 or 15 days to regulatory authorities in compliance with local and regional law. If so, the Sponsor (or the Sponsor's representative) will report the event to the appropriate regulatory authorities. The Investigator will report SAEs to the Institutional Review Board (IRB) per their IRB policy.

